We anticipate recruiting 1,200 (600 in each group) pregnant women into the study (see section 11.2 for sample size calculation); this is expected to yield a sufficiently large sample of children later in the study. Women will be recruited from 120 clusters (randomly assigned to intervention or control) that will be drawn from from Kimilili and Webuye districts in Bungoma County in Western Province of Kenya.

The communities will be informed about the study in village meetings by CHVs and by conducting outreach within their catchment area to identify pregnant women. Pregnant women will then be screened by 1AF enumerators. During **screening**, a few questions on health status and pregnancy will be asked. If the woman is prior or equal to 20 weeks of gestation (according to last menstrual period), has no visible severe disease and no allergy to peanuts or milk products, and confirms anticipated residence in the area for the coming 30 months, written informed consent for her and her offspring will be sought from her. She will then be asked to provide a urine sample to confirm pregnancy and she will be enrolled if pregnancy is confirmed. Following the screening, 5 assessment rounds (baseline and 4 follow-up assessments during the intervention) will be conducted at the participant's homes (rounds 1-3) or at a central place (rounds 4 and 5) within walking distance from their homes (Figure 2). Assessment round 3 (immediately) after delivery will be conducted as home visits or clinic visits in case of delivery at a clinic. Details of assessment procedures for each round are illustrated in (Figure 3).

Round 1 (Enrolment, ≤ 20 wk of gestation):

On the day of enrolment the round 1 assessment will be done. As part of this, the following information will be collected: household demographics and characteristics, maternal education; knowledge, attitude and practices (KAP) of specific dietary and nutrition practices during pregnancy; individual dietary diversity; antenatal care; WASH practices; height, weight and mid-upper arm circumference; maternal haemoglobin concentration and malaria parasitaemia from a capillary blood sample. After round 1, participants randomly allocated to the intervention group will start receiving the intervention package.

Round 2 (Gestational age of 34 ± 1 wk):

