(LMP: last menstrual period; GA: gestational age; ICD: informed consent document; MUAC: mid-upper arm circumference; Hb: haemoglobin; RDT: rapid diagnostic test (for malaria); HH: household; SES: socioeconomic status; KAP: knowledge, attitude and practice; ANC: antenatal care; WASH: water, sanitation and hygiene; MN: micronutrients; HC: head circumference; IYCF: infant and young child feeding)

The detailed procedures of study 1 are summarized in Table 3 below.

Table 3: Study 1 summary table of procedures and assessments

Study Periods	Screening		Intervention Period			
Visit/Round	0	1	2	3	4	5
Time (hour, day, week)	≤20 wk GA	≤20 wk GA	34±1wk GA	Delivery +48h	Infant 6.5±1 mo old	Infant 24±1 mo old
Randomisation of clusters (done prior to recruitment)						
Oral consent for screening questions	x					
Pregnancy and health status questions	x					
In- /exclusion criteria	x					
Written participant information and informed consent		x				
Pregnancy test		x				
Re-assessment of in- /exclusion criteria		x				
Household demographics/characteristics		x				
Maternal education		x				
Maternal anthropometry		x	x	x	x	
Child anthropometry				x	x	x
Capillary blood sampling in women		x	x		x	
Capillary blood sampling in children				x	x	x
Ante-/postnatal care		x	x	x	x	
Dietary and nutrition practices KAP, dietary diversity (pregnancy, lactation)		x	x		x	
WASH practices		x	x		x	x
Delivery information (incl. breastfeeding, birth weight and length)				x		
Breastfeeding and other IYCF indicators					x	x
Child dietary diversity					x	x
Child morbidity					x	x
Intervention adherence			x	x	x	x

Study 2:

General study design: Study 2 is a cluster-randomized, parallel-group, prospective, follow-up effectiveness study over a period of 2 years comparing 2 groups of children 6-35 months of age at recruitment:

- a) Intervention group: All selected households with children 6-35 months of age at recruitment will receive MNP (1 sachet every three days per child) and ORS along with zinc (20 mg/day) for treatment of acute diarrhoea. The households will also be provided with soap, chlorine solution, poultry (8 chickens at start of intervention), and seeds for red onion and indigenous greens (March 2018 and March 2019). The products will be accompanied by monthly nutrition and WASH trainings. The products and trainings will be provided free of charge. Additionally, all households will receive the agricultural package as in the control group.

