7.3 Study population

7.3.1 Eligibility criteria

Participants fulfilling all of the following **inclusion** criteria are eligible for the study:

Study 1:

- Pregnant women (≥ 18 years of age) with gestational age ≤ 20 weeks
- Written Informed Consent as documented by signature

Study 2:

- Children 6-35 months of age at recruitment
- Written Informed Consent as documented by signature

The presence of any one of the following **exclusion** criteria will lead to exclusion of the participant

Study 1:

- Family does not intend to stay within the study area for at least the following 30 months
- Known history of allergy towards peanut or milk products
- Visible severe disease

Study 2:

- Family does not intend to stay within the study area for at least the following 24 months

- Visible severe disease

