7.4 Interventions

LNS (Enov' Mum) (to be provided to pregnant women and up to 6 months after delivery in intervention group in study 1)

Enov' Mum has been designed based on recommendations of WHO, World Food Programme (WFP) and UNICEF [11] and is produced by Nutriset. This lipid-based Ready-to-Use Food supplement for home fortification aims at improving the nutrition and health status of pregnant and lactating women by filling micronutrients gaps in a non-emergency context thereby improving the development of the foetus and the infant. Enov'Mum is composed of the following ingredients: vegetable oils (rapeseed, palm, soy) skimmed milk powder, sugar, whey powder, peanuts, soy isolate, maltodextrin (corn), stabilizer (fully hydrogenated vegetable fat, mono- and diglycerides), vitamin and mineral complex, and aroma. This product does not contain any genetically modified organism and does not contain any ingredients of animal origin, except dairy products. Enov'Mum will be provided in individual 20 g sachets (**Figure 4**) and pregnant and lactating women will consume one sachet per day containing essential fatty acids and one to two recommended daily allowances (RDA) of vitamins and minerals (**Table 6**).

As adherence to antenatal iron/folic acid supplementation in Kenya is low (with 30.1% receiving no iron at all during pregnancy, 65% receiving any, but of those 53% receiving it for less than 60 days) [3] supplementing the women with LNS additionally is not expected to have any negative effects, and WHO guidelines during emergencies even state that iron/folic acid supplementation does not need to be discontinued while multiple micronutrient supplements are provided [11]. The participating pregnant women will remain under the national antenatal care services and will be encouraged to attend those in the same way as non-study participants are.

Table 6: Composition of Enov'Mum per 20 g sachet

Nutrient	Unit	20 g LNS portion
Energy	kcal	120
Protein	g	2.6
Lipids	g	9.2
Linoleic acid	g	1.58
α -Linolenic acid	g	0.65
Vitamin A, RAE	mg	800
Thiamin (B1)	mg	1.4
Riboflavin (B2)	mg	1.4
Pyridoxine (B6)	mg	1.9
Cobalamine (B12)	μ g	2.6
Folate, DFE	μ g	600
Vitamin C	mg	55
Vitamin D	μ g	15
Vitamin E	mg	15
Calcium	mg	60
Copper	mg	1.15
Iodine	μ g	250
Iron	mg	20
Magnesium	mg	9
Phosphorus	mg	57
Potassium	mg	104
Selenium	μ g	30
Zinc	mg	10

Figure 4: LNS Enov'Mum (daily portion)

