Anthelmintic treatment (to be provided to pregnant women in intervention group once during the second trimester)

A single dose of 400 mg albendazole will be provided to all pregnant women in the intervention group during the second trimester (13-27 weeks of gestation).

LNS (Enov' Nutributter) (to be provided to children 6-24 months of age in intervention group in study 1)

Enov'Nutributter is a lipid based nutrient supplement produced by Nutriset and designed to promote infant growth, motor development and to prevent malnutrition in children 6-24 months of age. Its micronutrient content is especially calculated to meet the needs of a child in this age group (see Table 7 for the composition). Enov'Nutributter is a paste based on peanuts, sugar, vegetable fat, skimmed milk powder, maltodextrin and whey, enriched with a vitamin and mineral complex and can either be consumed directly or added to the complementary food. Enov'Nutributter will be provided in individual 20 g sachets (Figure 5) and caregivers will be instructed to feed one sachet per day..

Table 7: Composition of Enov'Nutributter per 20 g sachet

Nutrient	Unit	20 g LNS portion
Energy	kcal	107
Protein	g	2.6
Lipids	g	6.9
Linoleic acid	g	1.15
α -Linolenic acid	g	0.27
Calcium	mg	60
Phosphorus	mg	86
Potassium	mg	152
Magnesium	mg	16
Zinc	mg	4
Copper	mg	0.2
Iodine	μ g	250
Iron	mg	9
Iodine	μ g	90
Selenium	μ g	10
Vitamin A, RAE	mg	400
Vitamin C	mg	30
Thiamin (B1)	mg	0.3
Riboflavin (B2)	mg	0.4
Pyridoxine (B6)	mg	0.3
Cobalamine (B12)	μ g	0.5
Folic acid	μ g	80
Pantothenic acid	mg	1.8
Niacin	mg	4
Sodium	mg	<58

Figure 5: LNS Enov'Nutributter (daily portion)

MNP (MixMe) (to be provided to children 6-59 months of age in intervention group in study 2)
 The MNP (MixMe™) to be used is produced by the company DSM according to recommendations by WHO [12] and distributed by UNICEF and WFP with the aim to improve diet quality of nutritionally vulnerable groups, such as young children [47]. MNPs are dosed into sachets (Figure 6) containing the dry powder with micronutrients that can be added to any semi-solid or solid food that is ready for consumption.

MNP will be provided in individual 1g sachets, which consist of the micronutrients as in Table 8. Children will consume 1 sachet every three days (120 days/year).

Table 8: Vitamin and mineral content in a 1 g sachet of MNP

Nutrient	Unit	MNP (1g portion)
Vitamin A, RAE	mg	400
Thiamin (B1)	mg	0.1
Riboflavin (B2)	mg	0.5
Niacin (B3)	mg	6
Pyridoxine (B6)	mg	0.5

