Soap (to all intervention households during the whole intervention period in both studies)
One 600 g bar of local soap will be provided per household per month.

Raw eggs (to all intervention households in study 1)
Raw eggs will be provided to the households during the whole duration of study 1. Pregnant and lactating women up to 6 months post-partum will receive 30 eggs every 2 weeks and will be encouraged to eat 2 eggs per day. Once the child turns 6 months, the families will receive 15 eggs every 2 weeks and the mothers will be encouraged to feed the child 1 egg per day. The eggs will be purchased regularly from carefully selected and monitored suppliers. All suppliers are approved by the County Public Health Officer and have food handling certificates. Additionally, all warehouse staff have food handling certificates. The warehouse where the eggs are stored has been assessed by the Public Health Officer and recommendations taken into account and modifications made. Approval has been given to store eggs in the climate-controlled section of the warehouse. The eggs will be distributed to the women every other week. The eggs will be distributed every other week in order to make sure only fresh eggs are consumed which should not pose any risk to the participants. The participants will further be sensitized on the dangers of consuming raw eggs and advised to always boil/fry the egg before consumption and the need of hygiene when preparing dishes containing eggs. As the regular consumption of eggs is not common, the benefits of egg consumption will be explained to the mothers. Adherence to egg consumption will be monitored by interviewing the mothers monthly.

Poultry (to all intervention households in study 2)
All intervention households in study 2 will receive 8 birds of chicken when they receive their first bundle of products. Chickens that have died from disease or accident will be replaced the following year.

Nutritionally enhanced seeds (to all intervention households in study 2)
Seeds for red onion and indigenous greens (managu and sukuma), all traditionally bred, will be provided to enrolled households in study 2 in March 2018 and March 2019 to align with planting. Red Onions and Sukuma Wiki seeds will be supplied by East African Seed based in Nairobi and Managu seeds will be supplied by Kenya Seed Company based in Kitale, Kenya.

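### The Study 1 allergy exclusion names only peanut and milk, although the package also supplies daily eggs and a soy-containing maternal LNS, so a woman with a known egg or soy allergy qualifies as written

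*Protocol*

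**What the plan says.** **Eligibility.** Section 7.3.1 of the protocol lists three exclusions for Study 1: planned departure from the area, visible severe disease, and "Known history of allergy towards peanut or milk products". The screening description in 7.1 asks that the woman "has no visible severe disease and no allergy to peanuts or milk products". Section 7.3.2 then takes in every pregnant woman who meets the criteria until the cluster target is reached. Table 3 has one further row, "Re-assessment of in- /exclusion criteria", marked once, at round 1.

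**Foods supplied to the intervention arm (7.1 and 7.4).**
- Eggs for the woman, from pregnancy to 6 months post-partum: she "will receive 30 eggs every 2 weeks and will be encouraged to eat 2 eggs per day".
- Eggs for the child from 6 to 24 months: "the mothers will be encouraged to feed the child 1 egg per day".
- Maternal LNS (Enov'Mum), one sachet a day, whose ingredients include "vegetable oils (rapeseed, palm, soy) skimmed milk powder, sugar, whey powder, peanuts, soy isolate, maltodextrin (corn".
- Child LNS (Enov'Nutributter), one sachet a day from 6 months, which "is a paste based on peanuts, sugar, vegetable fat, skimmed milk powder, maltodextrin and whey".

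**After enrolment.** Section 7.1 provides for monthly collection of adherence and morbidity data, and 7.4 for monthly interviews on egg consumption and home counselling twice a month. Section 7.3.3 discontinues participants for a clinically significant adverse event, or for another condition that prevents continued participation.

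**The concern.** The protocol accepts a principle: a woman with a known allergy to a food that the trial hands out should not be enrolled. It applies that principle to two of the LNS ingredients and not to the other foods in the same package. Egg is absent from the criterion although it is supplied for daily use to both mother and child. Soy is absent although the maternal LNS contains it in two forms.

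The child is a second gap. The question is put to the woman at or before 20 weeks of gestation, and the criteria are re-assessed only at round 1, before the child is born. The child later receives peanut and milk, the two allergens screened for in the mother, together with egg.

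What is at stake is participant safety and the fit between a stated rule and the products it is meant to cover. Section 7.4 discusses egg safety in terms of suppliers, storage, freshness and cooking, but not allergy. None of the five safety objectives in 4.4 concerns allergic reactions.

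**Working it through.** **1. Is egg exposure really daily?** Inputs are the deliveries in 7.4.
- Woman: 30 eggs / 14 days = 2.14 a day, against 2 a day encouraged.
- Child: 15 eggs / 14 days = 1.07 a day, against 1 a day encouraged.

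Supply matches the encouraged intake, so daily egg is a planned part of the package for both. These are amounts supplied and encouraged, not amounts eaten.

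**2. Criterion set against ingredients.**

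| Food or allergen | Woman offered it (7.4) | Child offered it (7.4) | In the maternal exclusion (7.1, 7.3.1) |
|---|---|---|---|
| Peanut | yes | yes | yes |
| Milk | yes | yes | yes |
| Egg | yes | yes | no |
| Soy | yes (oil and isolate) | not named in the child LNS | no |

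For the woman, two of the four rows are uncovered. For the child, the text shows no allergy check on any row.

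**3. Does another rule catch the woman?** The exclusion for visible severe disease does not reach an allergy with no current signs. The round 1 re-assessment uses the same criteria, so it cannot add egg or soy. Section 7.3.2 includes all who meet the criteria. A known egg or soy allergy therefore does not bar enrolment.

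**4. How many women?** The protocol gives no prevalence. As an assumption only, suppose 0.1% to 1% of women have a known egg or soy allergy.
- Intervention arm: 600 × 0.001 = 0.6 to 600 × 0.01 = 6 women.
- Both arms, if excluded: 1,200 × 0.001 = 1.2 to 1,200 × 0.01 = 12 women.

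**5. Could it matter for the analysis?** Section 7.3.3 plans for 46% non-consent and dropout before 24 months. The factors in 7.2 reproduce this: 1 − 0.95 × 0.80 × 0.95 × 0.75 = 1 − 0.5415 = 0.4585. Per arm that is 600 × 0.4585 = 275. Even if all 6 women at the upper assumption were lost, they would be 6 / 275 = 2.2% of the loss already planned for.

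**The case against.** The best reply is that the protocol does not contradict itself on the criterion: 7.1 and 7.3.1 name the same two foods, and nowhere does the protocol promise to exclude every allergen supplied. Eggs are an ordinary food which women are only encouraged to eat, so a woman who knows she is allergic can leave them. Several contacts follow enrolment, and a study physician is available. This lowers the likely harm. It does not close the gap, because these contacts are described as adherence, counselling and morbidity visits that follow supply of the products, and discontinuation follows an event. The soy is inside a sachet, so a woman may not know to avoid it.

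A second reply is that the enrolment, round and monthly forms and the consent texts (Appendices 14.1 and 14.2), and some text between 11.2 and 12.2, are not visible. An allergy question or warning could sit there. This stands for the child. It does not rescue the maternal criterion: a question on a form cannot exclude a woman on a ground that 7.3.1 does not contain.

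Stronger readings are tempting, and the documents do not support them.
- A reader might infer that allergic participants will be enrolled and will consume these foods. The text shows only that they can be enrolled and offered them.
- A reader might infer that the child's allergy is never checked. Only the absence of a check in the visible text can be stated.
- A reader might infer that the child LNS also contains soy. Its ingredient list does not name it.
- A reader might infer arm-specific loss that biases the result, since only intervention participants receive these foods, discontinued participants have no specific further assessments (7.3.3), and subjects without a paired measurement are left out (9.2.4). The mechanism exists, but the numbers are too small to claim an effect, and 7.3.3 does not say that an allergic reaction counts as clinically significant.
- A reader might expect a child question before 6 months to find most allergic children. The programme promotes exclusive breastfeeding until then, so there would be little known history to report.

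**Conclusion.** The point holds as a mismatch between the Study 1 allergy criterion and the foods in the package. A woman with a known egg or soy allergy meets all criteria as written and can be enrolled and offered daily eggs and a soy-containing LNS. In addition, the visible text sets no allergy check for the child before peanut- and milk-based LNS and eggs begin at 6 months. This second part is conditional on what the unseen forms contain.

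The size is small in numbers: roughly 1 to 6 intervention women under an assumed 0.1% to 1%, a range with no basis in the protocol. The count of offered women is an upper figure for actual intake. The ground is participant safety and internal consistency. No material effect on power, sample size or the primary estimate is claimed.

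**What to change.** 1. Reconcile the allergy criterion in 7.1 and 7.3.1 with the ingredients of every food supplied in 7.4, so that it addresses egg and soy as well as peanut and milk.
2. Ask the question identically in both arms. Clusters are randomised before recruitment (Table 3), so a question put only in intervention clusters would make the eligible populations differ by arm.
3. State in the protocol whether and how the child's allergy is ascertained before child products start. If a form already does this, refer to it.
4. The management of any participant with an allergy is for the investigators to define; none is proposed here.

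The cost is an edit to one criterion in two places, a matching change to the screening question, and a statement on the child. A few women become ineligible, 1.2 to 12 of 1,200 under the assumption above. Because 7.3.2 recruits until each cluster's target is reached, others in the cluster may fill those places.

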7.3.2 Recruitment and screening

Study 1:

During community meetings and outreach CHVs will inform and 1AF field officers will screen potential participants. In case a woman declares to be pregnant, oral consent for a screening assessment including providing the date of last menstrual period and checking for inclusion/exclusion criteria will be taken. If woman is eligible written informed consent will be sought and the woman will be asked to provide a urine sample for a pregnancy test. Women will be enrolled in case pregnancy is confirmed. All pregnant women meeting all the inclusion/exclusion criteria will be included in the study until the anticipated sample size in each selected cluster is reached.

Study 2:

Household lists of farmers participating in the 1AF programme will be used to determine whether a household has at least one eligible child between 6-35 months of age. A child will be included once inclusion and exclusion criteria have been checked and written informed consent is obtained from the caregiver. The baseline assessment will then be conducted. 1AF field officers will be responsible for recruiting the selected children.

7.3.3 Criteria for withdrawal/discontinuation of participants

Study 1:

Pregnant women are free to withdraw themselves or their children from participation in the study at any time. If the pregnant woman is being diagnosed with severe anaemia (haemoglobin (Hb)<70g/L) or severe acute malnutrition (MUAC < 23 cm) at round 1, she will be excluded from participation and will be referred for treatment according to national guidelines to the nearest health centre. If the pregnant woman is being diagnosed with malaria parasitaemia and has an axillary temperature of >37.5°C in round 1, she will be referred for treatment but will continue participating in the study after temporary suspension from interventions if required as assessed by the study physician. If the pregnant woman has an Hb between 70 and 109 g/L in rounds 1 or 2, she will be advised by the study team to go to the hospital for further management. This will be facilitated by CHVs. If the mother, infant or child is being diagnosed with malaria parasitaemia and an axillary temperature of >37.5°C, or severe anaemia (Hb<70g/L), or they suffer from severe acute malnutrition (WHZ<-3 and/or bilateral oedema for child, MUAC < 23 cm for mother) in rounds 2 to 5, affected participants will be referred for treatment according to national guidelines but will continue in the study after temporary suspension from interventions if required as assessed by the study physician. If a child is born with low birth weight (<2500 g) and/or has a Hb < 135 g/L, he/she will be referred for a medical check. Further, study participants will be discontinued from participation in the study in case of any clinical significant adverse event (AE), or any other medical condition or situation that prevents continued participation in the study. If a participant is discontinued no specific follow-up assessments will be conducted other than the follow up until resolution in case of exclusion due to a serious adverse event (SAE). Participants will not be replaced, as a non-consent and dropout rate of 46% prior to reaching 24 months of age is included in the sample size calculation.

Study 2:

Caregivers are free to withdraw their children from participation in the study at any time. If a child is being diagnosed with severe acute malnutrition (WHZ<-3 and/or bilateral oedema) at round 1, he/she will be excluded from participation and will be referred for treatment according to national guidelines to the nearest health centre. If a child suffers from severe acute malnutrition (WHZ<-3 and/or bilateral oedema) in rounds 2 and 3, affected participants will be referred for treatment according to national guidelines but will continue in the study after temporary suspension from interventions if required as assessed by the study physician. Further, study participants will be discontinued from participation in the study in case of any clinical significant adverse event (AE), or any other medical condition or situation that prevents continued participation in the study. If a participant is discontinued no specific follow-up assessments will be conducted other than the follow up until resolution in case of exclusion due to a serious adverse event. Participants will not be replaced, as a non-consent and dropout rate of 24% prior to the final assessment after 2 years is included in the sample size calculation.

